4.7.1 Adverse Events

All treatment emergent adverse events (TEAEs) will be reported. A TEAE is defined as an AE that occurs on or after the date of the first column use.

A summary of all TEAEs, as reported in the EDC, by the number and percentages of subjects who experienced any of the following will be provided for the Safety population:

- Any TEAE, including severity (Mild, Moderate, and Severe), relationship to study device and procedures (Unrelated, Possibly Related, Definitively Related), TEAEs leading to discontinuation of study participation.
- Any serious adverse events (SAEs), including severity (Mild, Moderate, and Severe), relationship to study device and procedures (Unrelated, Possibly Related, Definitively Related), SAEs leading to discontinuation of study participation
- Any ADEs, including severity (Mild, Moderate, and Severe), relationship to study procedures (Unrelated, Possibly Related, Definitively Related), ADEs leading to discontinuation of study participation
- Any fatal TEAEs, including relationship to study device and procedures (Unrelated, Possibly Related, Definitively Related)

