4.2. Study Endpoints

4.2.1. Primary Endpoints

- Safety and tolerability of each column size and each blood-flow rate.
 - Evaluation of safety and tolerability will include assessment of the rate and severity of all AEs, with analyses of ADEs, TEAEs, number of IDH events, and changes in total and free Hgb.
 - O Tolerability will be assessed by the proportion of subjects who can escalate to and tolerate each column size and blood-flow-rate combination.

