8.4. Reporting Procedures

8.4.1. Adverse Event Reporting

All subjects who have given informed consent will be evaluated for AEs. All AEs that occur after initiation of treatment with the column will be considered TEAEs. Subjects with TEAEs must be followed until the AE/ADE is resolved or is stable, unless the subject is lost to follow up.

Each AE/ADE must be described as follows: the date of onset, date of resolution, severity (mild, moderate, severe), frequency of the event (single episode, intermittent, continuous), action taken with study device (no action taken, device discontinued), outcome, relationship to study device* (unrelated, possibly related, definitely related), and seriousness criteria. Each AE/ADE must be recorded separately.

*Note: Assessment of the relationship to study device will be made only when the AE occurs after the subject has initiated at least one (1) treatment with the column. An AE occurring before the subject's exposure to the column will always be labeled as "unrelated."

Any AE/ADE or SAE/SADE occurring during the study must be documented in the subject's source documentation and as an AE/ADE in the CRF. All SAE/SADEs should be reported to the Sponsor according to the reporting timeframes specified in Section 8.4.2.1.

[figure not shown]
The investigator should attempt to establish a diagnosis of the event (that meets the definition of an AE/ADE or SAE/SADE) based on signs, symptoms, and/or other clinical information. In such cases, the diagnosis should be documented as the AE/ADE and/or SAE/SADE and not the individual signs or symptoms. The diagnosis will become the basis for the verbatim term as reported by the investigator. If no diagnosis is known and clinical signs and symptoms are not present, the abnormal finding should be recorded.

In addition to the investigator's own description of the AE/ADE, each AE/ADE will be encoded according to the Medical Dictionary for Regulatory Activities (MedDRA). The investigator will take all appropriate and necessary therapeutic measures required for resolution of and AE/ADE. Any medication necessary for the treatment of an AE/ADE must be recorded on the concomitant medication CRF.

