10.4.2. Analysis of the Primary Endpoint

Safety and tolerability will be evaluated by examining the occurrence of TEAEs and AEs leading to de-escalation and/or discontinuation from the study and by the number of subjects who are able to complete each phase (i.e., a column size at both blood-flow rates).

Summary tabulations of the reported AEs will be presented by column size after the verbatim terms have been coded to preferred terms (PTs) and system organ classes (SOCs) using the MedDRA Version 23.0 coding dictionary or higher. The summaries will include severity and attribution to the study device. Multiple reports of the same AE by the same subject will be counted only once at the highest severity and strongest attribution to the study device.

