2.3 Primary Endpoint

- Safety and tolerability of each column size and each blood-flow rate.
 - Evaluation of safety and tolerability will include assessment of the rate and severity
 of all treatment emergent adverse events (TEAEs), with analyses of adverse device
 effects (ADEs), number of intradialytic hypotensive (IDH) events, and changes in
 total and free hemoglobin (Hgb).
 - O Tolerability will be assessed by the proportion of subjects who can escalate to and tolerate each column size and blood-flow-rate combination.

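### The TEAE definition has no worsening clause, so an adverse event that starts between consent and Day 1 and worsens on the column may be missing from the TEAE and ADE tables (minor, cheap to fix)

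*SAP*

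**What the plan says.** **TEAE definition.** SAP 4.7.1 (Adverse Events): "A TEAE is defined as an AE that occurs on or after the date of the first column use". Protocol 8.4.1 (Adverse Event Reporting): "All AEs that occur after initiation of treatment with the column will be considered TEAEs". Neither mentions a change in severity or seriousness of an event already present.

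**AE record.** Protocol 8.4.1 requires for each event "the date of onset, date of resolution, severity (mild, moderate, severe"), and "frequency of the event (single episode, intermittent, continuous"). So a record has one onset date and one severity, and may describe an event that continues. Section 8.4.1 asks for separate records for separate events, but does not say that a worsening opens a new one.

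**Relatedness.** Protocol 8.4.1: "An AE occurring before the subject's exposure to the column will always be labeled as" unrelated. Under protocol 8.1.1 an ADE is an AE judged related to the device, so such a record cannot be an ADE.

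**Collection window.** AEs are collected from consent (protocol 7.1.1.1). Screening runs from Day -35 to Day -7 and run-in from Day -6 to Day -1 (SAP 3.6).

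**Outputs.** The protocol's primary endpoint (4.2.1) calls for "assessment of the rate and severity of all AEs". SAP 2.3 words this as the rate and severity "of all treatment emergent adverse events (TEAEs), with analyses of adverse device" effects. SAP 4.7.1.1, 4.7.1.2 and 4.7.1.4 tabulate TEAEs, serious TEAEs and ADEs. All AEs and all SAEs are listed with a TEAE flag.

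**The concern.** The severity and device-attribution tables for the primary safety endpoint are built entirely on the TEAE and ADE classes. Whether the column aggravates a complaint that arose during screening or run-in is part of the tolerability question, and the run-in itself changes care: subjects used to 400-500 mL/min (protocol 5.1) are dialyzed at 250 mL/min.

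Take, as an illustration, a mild headache first reported in run-in that becomes severe on the S-25 column. If the site updates the existing record, its onset date still precedes Day 1 and its relationship stays unrelated. A flag set from onset date then drops it from every summary of severity and attribution, although the worsening happened on the column. With up to four sites, the same course could be counted at one site and left out at another, depending on local recording habits.

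**Working it through.** The plan gives no figure on this point to reproduce. The check is a reading of the rules in sequence, followed by arithmetic for scale.

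**Step 1: follow one event through the rules.** It starts between consent and Day 1, is ongoing, is kept as one record, and worsens on the column.

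| Rule | Result |
|---|---|
| SAP 4.7.1, TEAE by when the AE occurs | Not a TEAE if the flag uses onset date, the only start date that 8.4.1 requires |
| Protocol 8.4.1, pre-exposure AE | Labeled unrelated |
| Protocol 8.1.1, ADE must be judged related | Not an ADE |
| SAP 4.7.1.1, 3 TEAE tables | Not counted |
| SAP 4.7.1.2, 3 serious-TEAE tables | Not counted, even if it becomes serious |
| SAP 4.7.1.4, 3 ADE tables | Not counted |
| SAP AE and SAE listings | Shown, flagged as not a TEAE |

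Tables by system organ class and preferred term: 3 + 3 + 3 = 9. Six are restricted to TEAEs and three to ADEs; none covers all reported AEs. The SAE line in the SAP 4.7.1 overview does not repeat the TEAE restriction, but it sits within a summary of TEAEs, so it probably does not help.

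**Step 2: remove what is caught elsewhere.**
- Conditions present before consent are not recorded as AEs (protocol 7.1.1.1), so their worsening on the column is a new AE and hence a TEAE.
- IDH counts, hemoglobin changes, and de-escalation and discontinuation counts (SAP 4.7.2 to 4.7.4) do not use the TEAE flag. Nor do the critical laboratory values (SAP 4.9.5).

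What remains is mainly non-serious worsening of AEs whose onset lies in the window from consent to Day -1, at most 35 days.

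**Step 3: scale.** One omitted subject moves an incidence by 100/15 = 6.7 percentage points with 15 subjects, or 100/12 = 8.3 with 12. A preferred term seen in that subject alone would show 0/15 instead of 1/15.

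The documents give no rate for such events. As an assumption only, let p be the chance per subject. The expected number among 15 is 15p, and the chance of at least one among n subjects is 1 - (1 - p)^n.

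| Assumed p | Expected, n = 15 | At least one, n = 15 | At least one, n = 12 |
|---|---|---|---|
| 0% | 0 | 0% | 0% |
| 2% | 0.3 | 26% | 22% |
| 5% | 0.75 | 54% | 46% |
| 10% | 1.5 | 79% | 72% |

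These rows only restate the assumed p. They are not evidence that such events will occur.

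**The case against.** The best reply is that both definitions speak of an AE that occurs, not of its onset. The AE definition in protocol 8.1.1 is broad enough for a worsening to be an event of its own, protocol 8.3 prompts sites to ask about changes at each visit, and separate events get separate records. A site following this would enter a new AE, which would be a TEAE open to a relatedness assessment. CRF instructions that are not part of these documents may say so. That stands as far as it goes: the text allows a new record but does not require one. Eligibility also asks for at least 4 weeks of stable health before screening, the study is descriptive, and every AE is listed.

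Three stronger readings are tempting and not supported.

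- *Aggravation of any existing disease is lost.* It is not. As shown above, only AEs first arising between consent and Day 1 are exposed.
- *The SAP departs from protocol 10.4.2.* That section does say "Summary tabulations of the reported AEs will be presented by column size", but its opening sentence already evaluates safety through TEAEs and through AEs leading to de-escalation or discontinuation. The difference in endpoint wording between protocol 4.2.1 and SAP 2.3 is real, but it matters here only because no table of all AEs is left as a backstop.
- *The halting rule in protocol 8.5 would miss device harm.* A serious deterioration meets the SAE definition (8.1.2), and the SAE form carries its own onset date and device relationship (8.4.2.2). Doubtful cases lean towards related (8.1.1), the sponsor may also judge an event related (8.2.2), and 8.5 has a pattern trigger besides the count. A gap would need all of these to fail.

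**Conclusion.** The gap is real, narrow and minor. It rests on two assumptions: that a site keeps the worsening event as one record, and that the TEAE flag is programmed from onset date. The documents neither require nor exclude the first; the second is the most likely programming given the data that 8.4.1 collects. Where both hold, the on-column worsening is absent from the TEAE and ADE tables and visible only in listings. The listings would show the record, but 8.4.1 does not require the date on which it worsened. The number of affected events cannot be derived and may be zero. In a study of about 15 subjects, though, a single one decides whether a preferred term appears in the tables at all. No result is shown to be wrong, and the point is worth making because the correction is standard and cheap.

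**What to change.** In both SAP 4.7.1 and protocol 8.4.1:

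1. Define a TEAE as an AE with onset on or after first column use, or an AE with earlier onset that increases in severity or becomes serious on or after first column use.
2. Require a new AE record at that worsening, with its own date, severity and device-relationship assessment.
3. Limit the automatic unrelated label to the course of the event before exposure.

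Changing the SAP alone would not be enough: the event would enter the TEAE tables, but the protocol's label would still keep it out of the ADE tables. The cost is about one sentence on the definition in each document, the matching edits to 8.4.1, a CRF completion instruction, and a few more AE records.

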4.7.1.1 Summary for All TEAEs

The number and percentage of subjects who experience TEAEs will be tabulated by SOC and PT using the MedDRA version 23.0 or higher. Adverse events will be counted only once for a subject within each PT and SOC at the highest severity and strongest attribution to the study device; thus, since a subject may have more than one PT within a SOC, percentages of PT may not sum to the percentages in the SOC.

For all TEAEs the following will be summarized:

- Overall summary of any TEAEs presented by SOC/PT
- Overall summary of any TEAEs by worst severity presented by SOC/PT
- Overall summary of any TEAEs by most causal relationship to device and procedures presented by SOC/PT

A Listing of all AEs will be provided. This listing will include a flag identifying if an AE is a TEAE.

4.7.1.2 Summary for Serious TEAEs

For all serious TEAEs the following will be summarized:

- Overall summary of any serious TEAEs presented by SOC/PT
- Overall summary of any serious TEAEs by worst severity presented by SOC/PT

 Overall summary of any serious TEAEs by closest relationship to device and procedures presented by SOC/PT

A Listing of all serious AEs will be provided. This listing will include a flag identifying if a serious AE is a TEAE.

4.7.1.3 **Deaths**

Deaths, if any, will be provided in a listing only.

4.7.1.4 Summary for Adverse Device Effects

The number and percentage of subjects who experience any ADEs will be tabulated by SOC and PT using the MedDRA version 23.0 or higher.

An ADE will be counted only once for a subject within each PT and SOC at the highest severity and strongest attribution to the study device; thus, since a subject may have more than one PT within an SOC, percentages of PT may not sum to the percentages in the SOC.

For all ADEs the following will be summarized:

- Overall summary of any ADEs presented by SOC/PT
- Overall summary of any ADEs by worst severity presented by SOC/PT
- Overall summary of any ADEs by most causal relationship to procedures presented by SOC/PT

A Listing of all ADEs will be provided.

4.7.2 IDH Events

The number and percentage of subjects will be summarized for the Safety, Evaluable and PP populations, by column size and blood-flow rates combination, for the following:

- Historical IDH Rate (0,1,2,3,4)
- Number of IDH Events (0, 1, 2, 3, 4, 5, 6)
- Change in IDH Rate above the Historical IDH Rate (0, 1, 2, 3)

A listing of IDH Rate, including each subject's historical IDH rate and number of hypotensive events, will be provided.

Protocol Defined IDH Definitions:

Statistical Analysis Plan AKST1210-101

Rev. A Page 16 of 28

Intradialytic hypotension/hypotensive event (IDH)

A systolic blood pressure (SBP) < 90 mmHg that occurs during hemodialysis and is confirmed by repeat measurement.

Expected IDH Rate

The expected number of occurrences of IDH per weekly treatment period derived from a subject's Historical IDH rate (see section below and Protocol Appendix 17.1). The expected IDH Rate is compared

with the actual IDH rate and used to assess escalation, de-escalation, and discontinuation.

Historical IDH Rate

The number of occurrences of IDH as documented in a subject's medical record during a recent 8-week period prior to the run-in period. Subjects with 7 or more IDH events during this 8-week interval will be excluded.

4.7.3 Change in Total and Free Hemoglobin

Plasma levels of total Hgb and free Hgb at baseline (i.e., the last nonmissing value prior to the start of HD with the column) and each scheduled post-baseline timepoint, along with change from baseline at each scheduled post-baseline timepoint will be summarized for the Safety, Evaluable and PP populations, by each column size and blood-flow rate combination and total.

A listing of total and free Hgb level, as well as the changes from baseline at each scheduled post-baseline timepoint will be provided.

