- 11. Clinically significant abnormalities on screening ECG including QT interval corrected for heart rate (QTc) using Fridericia's correction formula [QTcF] of ≥ 500 ms in men and ≥ 520 ms in women.
- 12. Delirium (encephalopathy).
- 13. Out of range value for complete blood count (CBC), complete metabolic panel, or coagulation that the investigator deems clinically significant.
- 14. Thyroid stimulating hormone (TSH) below 0.2 or above 6.0 mIU/L, and/or clinically-relevant abnormalities in T3 or T4.
- 15. Hemoglobin level < 9.0 g/dL.
- 16. Alanine aminotransferase (ALT) and/or aspartate transaminase (AST) > 3 times upper limit of normal.
- 17. Uncontrolled type 2 diabetes.
- 18. Concurrent or have recent participation in another interventional clinical trial. Prior clinical trial subjects must have discontinued investigational agents/devices at least 30 days prior to planned first use of the column.
- 19. History of severe depression/suicidality requiring hospitalization in the last 6 months.
- 20. Significant drug or alcohol abuse within the past 12 months.
- 21. Patients planning to receive renal transplantation during the study.
- 22. Patients with any other condition and/or situation the investigator believes may interfere with the safety of the subject during study participation, study conduct, or interpretation of study data.

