7.1.1.1.5. Laboratory Evaluations

Blood samples will be collected and analyzed throughout the study. Blood will be drawn by a qualified medical provider. Laboratory evaluations will be completed by a central laboratory. Samples for screening laboratory evaluations should be collected either on a non-dialysis day or prior to HD. For additional information, refer to Section 15.3 Schedule of Laboratory Tests.

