15.3. Schedule of Laboratory Tests

Assessment	Screening	I	Run-i	n									Treat	tment]	Period								End of Study (EOS)
	V1	V2	V3	V4	V5	V6	V7	V8	V9	V10	V11	V12	V13	V14	V15	V16	V17	V18	V19	V20	V21	V22 (EOT)	V23
b2M/proteomics				X			X			X			X			X			X			X	X
Serum pregnancy (WOCBP only)	X			X																			X
Hematology						Note	: CBC	, Hp, I	Hgb, aı	nd plasr	na-free l	Hgb sho	uld be ta	aken AI	TER H	D V4-V	21.						
Complete blood count (CBC)	X					X			X									X			X		
Haptoglobin (Hp)				X		X			X									X			X		
Hemoglobin (Hgb)	X					X			X									X			X		X
Plasma-free Hgb				X		X			X									X			X		
Chemistry			Note	: BUN	and (Creatin	ine sh	ould b	e colle	cted BE	FORE a	and AFT	ER HD										
Alanine aminotransferase (ALT)	X											X											
Albumin	X											X											
Aspartate transaminase (AST)	X											X											
Bicarbonate (HCO ₃)	X											X											
Bilirubin (total)	X											X											
Blood urea nitrogen (BUN)	X		X			X			X			X			X			X			X		
Calcium (Total)	X						X															X	
Chloride (Cl)	X											X											
Creatine kinase (CK)	X																						
Creatinine	X		X			X			X			X			X			X			X		
Glucose	X						X					X										X	
Hemoglobin A1c (HbA1c)	X																						

Protocol AKST1210-101 V2.1 13MAY2021

Assessment	Screening	I	Run-ii	n									Treat	ment l	Period								End of Study (EOS)
	V1	V2	V3	V4	V5	V6	V7	V8	V9	V10	V11	V12	V13	V14	V15	V16	V17	V18	V19	V20	V21	V22 (EOT)	V23
Lactate dehydrogenase (LDH)	X																					(= 0 = 7	
Magnesium (Mg)	X																						
Potassium (K)	X											X											
Phosphate	X											X											
Protein (total)	X											X											
Sodium (NA)	X											X											
Coagulation																							
Activated partial thromboplastic time (aPTT)	X											X											
Prothrombin time (PT/INR)	X											X											
Serology																							
Hepatitis B surface/core antigen (HBsAg)	X																						
Hepatitis C antibody (HCV Ab)	X																						
Human immunodeficienc y virus antibody (HIV Ab, HIV1/HIV-2)	X																						
Other Clinical Labs	Note: All la section should						Note	: All la	ıbs in 1	he "Otl	ner Clini	cal Labs	s" sectio	n shoul	d be col	lected E	BEFORE	E and A	FTER H	D at V7	and V2	.22.	
Adrenocorticotro pic hormone (ACTH)				X			X															X	
Complement (total)(CH50)				X			X															X	
Complement C3 and C4				X			X															X	
Complement C5a				X			X															X	

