17.1.2. De-escalation Rules

The purpose of the de-escalation rules is to ensure the safety of a subject who is experiencing IDH, anemia or other safety issues that may be related to the column size.

A subject should be de-escalated if during the 1-week treatment period they experience the number of IDH events described in the table above and/or have an Hgb level < 9 g/dL despite receiving optimized treatment with ESA.

De-escalation will only be applicable at V11 through V19 as shown in Figure 4 below. Subjects who do not tolerate treatment with the S-15 column at any time prior to V11 or after V19 will be discontinued (see Section 17.1.13. Discontinuation Rules).

Figure 4. De-escalation Schematic

Subjects will continue with the same visit schedule after de-escalation. At the visit following confirmation of de-escalation, treatment will resume with the previous column size at the high flow rate (up to 450 mL/min).

- ➤ If de-escalation occurs during V11 through V16, subjects will resume treatment at the next scheduled visit with the S-15 column at up to 450 mL/min and will continue with this column size/flow rate combination through EOT (V22).
- ➤ If de-escalation occurs during V17 through V19, subjects will resume treatment at the next scheduled visit with the S-25 column at up to 450 mL/min and will continue with this column size/flow rate combination through EOT (V22).

Table 4 below illustrates the visit schedule for subjects who de-escalate. *Note*: the only change compared to Section 15 is column size and flow rate.

Table 4. Schedule of Events for Subjects Who De-escalate

					,	Treatm	ent Peri	iod					EOS
Visit Number	V11	V12	V13	V14	V15	V16	V17	V18	V19	V20	V21	V22 (EOT)	V23
Study Week		Week 3			Week 4	ļ	,	Week 5			Week	6	Week 7
Study Day(s) (± 1)	Day 15	Day 17	Day 20	Day 22	Day 24	Day 27	Day 29	Day 31	Day 34	Day 36	Day 38	Day 41	Day 43
Procedure													
Physical examination													X
12-lead ECG													X
Targeted physical examination	X	X	X	X	X	X	X	X	X	X	X	X	
Weight	X	X	X	X	X	X	X	X	X	X	X	X	X
Vital signs ¹	X	X	X	X	X	X	X	X	X	X	X	X	X
Laboratory tests ²		X	X		X	X	X	X	X	X		X	X
Column size			S-	15			S-15	OR S-2	.5 (if de	e-escala	ated aft	er V16)	
Hemodialysis blood-flow rate (mL/min)						Up	to 450						
Assessment of fluid status	X	X	X	X	X	X	X	X	X	X	X	X	
Kt/V assessment		X			X		_	X			X	X	_
Adverse events and concomitant medications	X	X	X	X	X	X	X	X	X	X	X	X	X

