8.3	Section content expanded as follows: Previously read: "At every clinic visit, subjects will be assessed for AEs and SAEs. After the subject has had an opportunity to spontaneously mention any problems, the investigator should inquire about AEs by asking a non-leading question such as the following: "How are you feeling?" "Have you had any changes since your last assessment/visit?" "Have you taken any new medicines since your last assessment/visit?"	Clarification of safety assessments and monitoring related to both procedures and personnel.
	• "At very clinic visit, subjects will be assessed for AEs and SAEs. All AEs and SAEs will be monitored and recorded by trained and knowledgeable personnel to protect subjects from harm. At the beginning of each visit, after the subject has had an opportunity to spontaneously mention any problems that may have occurred during the preceding interdialytic interval, the investigator should inquire about any possible interdialytic AEs by asking a non-leading question such as the following:	
	 "How are you feeling?" "Have you had any changes since your last assessment/visit?" "Have you taken any new medicines since your last assessment/visit?" During and for a period after each HD session, participating subjects will be closely 	
	monitored by qualified healthcare personnel who are trained in HD and who have experience in the types of AEs that typically occur during HD. Any events that occur during or after HD (before the subject leaves the clinic), will be assessed by the HD	

8.4.3 15.2	personnel (e.g. hemodialysis technician or nurse) and discussed as appropriate with the investigator or designee." Section heading included in error. The Kt/V assessment was removed from Visit 23 (EOS).	Section heading removed to correct error. Assessment of Kt/V is not necessary as HD is not included in Visit 23 (EOS).
15.3	Expanded note to indicate that plasma-free Hgb should also be taken AFTER HD V4-V21.	Clarification of timing of laboratory measurement.
17.1	The content in the initial paragraph was updated and expanded as follows: **Previously read:* "The purpose of the escalation rules is to ensure the safety of the subject when transitioning to a larger-size column, since the main risk of	Clarification of the purpose of the escalation rules and definition of IDH.
	Now reads: • "The purpose of the escalation rules is to ensure the safety of the subject when transitioning to a larger-size column. Since the main risk of	

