Baseline is the first value after the start of HD with the column. For the assessments that do not take place during the treatment weeks (e.g., ECG, physical examination, etc.), the value from Screening will be the baseline. Baseline for lab values will be the last non-missing value prior to the start of HD with the column.

Change from baseline is the post-treatment value minus baseline value.

Subjects who de-escalate (i.e., do not proceed to the next column size and blood-flow rate combination) will only be included in analysis up to the point of de-escalation.

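### Change in total hemoglobin, a primary-endpoint component, subtracts a screening value drawn before or away from dialysis from on-column values drawn after dialysis, so fluid removal can hide blood loss caused by the column.

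*SAP*

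**What the plan says.** - **Endpoint.** Protocol 4.2.1 lists among the primary safety measures the "number of IDH events, and changes in total and free Hgb". The primary endpoint in SAP 2.3 also includes both.
- **Baseline.** SAP 4.7.3 summarizes change from "Plasma levels of total Hgb and free Hgb at baseline (i.e., the last nonmissing value prior to the start of HD" with the column. The general rule in SAP 4.1 agrees: "Baseline for lab values will be the last non-missing value prior to the start of HD with the column".
- **Schedule.** In Protocol 15.3, total Hgb is marked at V1, V6, V9, V18, V21 and V23, and CBC at V1, V6, V9, V18 and V21. Neither is marked in the run-in (V2-V4). Haptoglobin and plasma-free Hgb are marked at V4, V6, V9, V18 and V21.
- **Timing at screening.** Protocol 7.1.1.1.5: "Samples for screening laboratory evaluations should be collected either on a non-dialysis day or prior to HD". Section 15.1 places screening at Days -35 to -7.
- **Timing on treatment.** The hematology note in 15.3 puts CBC, haptoglobin, Hgb and plasma-free Hgb after HD for V4 to V21. The note is broken in the extracted text but legible. The revision log in 18.1 describes the same instruction cleanly: "Expanded note to indicate that plasma-free Hgb should also be taken AFTER HD V4-V21".
- **Safety rules.** Exclusion 15 is "Hemoglobin level < 9.0 g/dL". Under 17.1.2 a subject should be de-escalated if they "have an Hgb level < 9 g/dL despite receiving optimized treatment with ESA". Section 17.1.1 requires at least 9 g/dL for escalation. None of the three states whether the sample is pre- or post-HD.

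**The concern.** Removing fluid during HD concentrates the blood, so Hgb is higher after a session than before it, whatever the column does. If the baseline is drawn before fluid removal and every on-column value after it, the planned change contains an upward shift unrelated to the device. The shift favors the device: it moves the table towards no fall, or a rise, and can cancel a real loss from hemolysis, clotting or blood left in the circuit.

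The V1 value is also old. It is drawn up to 35 days before first column use, and inclusion criterion 9 exempts anemia medication from the stable-dose requirement, so Hgb may drift in between.

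The same difference reaches the 9 g/dL limits. Eligibility is judged on the screening sample, while the scheduled on-column Hgb available for escalation and de-escalation is post-HD. De-escalation for anemia is itself counted as a tolerability outcome in SAP 4.7.4.

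**Working it through.** The plan gives no figure for Hgb. Its only design probability concerns intradialytic hypotension (1 - 0.9^12 = 0.718, against a stated 70% or so) and plays no part here.

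**Step 1: which value is the baseline?** Reading the 15.3 rows across the 23 visits:

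| Test | Scheduled visits | Last scheduled value before column use | Draw timing of that value |
|---|---|---|---|
| Total Hgb | V1, V6, V9, V18, V21, V23 | V1 | Non-dialysis day or pre-HD |
| CBC | V1, V6, V9, V18, V21 | V1 | Non-dialysis day or pre-HD |
| Plasma-free Hgb | V4, V6, V9, V18, V21 | V4 | Post-HD |
| Haptoglobin | V4, V6, V9, V18, V21 | V4 | Post-HD |

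Column use starts at V5, so V6 is already on the column. All four on-column Hgb timepoints (V6, V9, V18, V21) are post-HD and all are compared with V1. V23 lies outside the note, so its timing is unspecified.

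**Step 2: size of the shift.** The documents give no blood-volume change. Let d be the fractional fall in blood volume by the end of HD, with red-cell mass unchanged. Then

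post-HD Hgb = pre-HD Hgb / (1 - d).

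I assume d between 5% and 15%. With no device effect and a pre-HD Hgb of 10 g/dL:

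- d = 5%: 10/0.95 - 10 = +0.53 g/dL
- d = 10%: 10/0.90 - 10 = +1.11 g/dL
- d = 15%: 10/0.85 - 10 = +1.76 g/dL

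**Step 3: how much loss is hidden?** For baseline H and true loss L (both on the pre-HD scale), the planned change is (H - L)/(1 - d) - H, which is zero when L = H × d.

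- H = 10: losses of 0.5 (d = 5%) to 1.5 g/dL (d = 15%) show as zero.
- H = 10.5: losses of 0.53 to 1.58 g/dL show as zero.
- H = 10.5, L = 1.0: the table shows -0.50 at d = 5%, +0.06 at 10% and +0.68 at 15%.

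**Step 4: the 9 g/dL limit.** A pre-HD value of 8.5 g/dL reads 8.5/0.95 = 8.95 to 8.5/0.85 = 10.0 post-HD. It crosses 9 once d exceeds 1 - 8.5/9 = 5.6%. In the other direction, a post-HD reading of 9.0 corresponds to a pre-HD value of 9 × 0.95 = 8.55 down to 9 × 0.85 = 7.65 g/dL.

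**Step 5: the same comparison with a post-HD V4 baseline.** If d is similar at V4 and on the column, the change becomes -L/(1 - d). A true loss of 1.0 g/dL then shows as -1.05 to -1.18 g/dL, with the right sign and close to the right size.

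**The case against.** The strongest reply has four parts.

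1. **The SAP rule is sound and the gap is in the schedule.** The last value before column HD would be V4 automatically if Hgb were drawn there, and the 15.3 note already names CBC and Hgb in an instruction that starts at V4. A missing mark may be all that is wrong. That is a fair account of the cause, but the two documents as written still yield V1.
2. **The size is assumed.** No blood-volume figure is given, and rinse-back, prophylactic saline and the delay before sampling would all alter it. At the 5% end, 8.5 g/dL still reads below 9 and the rule still fires. This stands as a limit on the numbers. The timing mismatch and its direction under net fluid removal do not depend on them.
3. **Other measures would catch a loss.** Free Hgb and haptoglobin have a matched baseline, visible clotting is counted, clinically significant laboratory values become AEs, and contrasts between on-column visits are post-HD against post-HD. The flow-rate contrasts are indeed less affected. But none of these corrects the change-from-baseline table that 4.7.3 specifies. Free Hgb and haptoglobin do not measure blood retained in the circuit, and only a no-column reference can show a loss common to all column conditions.
4. **The effect on the safety rules is inferred.** The rules name no sample, and sites may run local tests. Within the V11-V19 de-escalation window, V18 is the only scheduled Hgb. This stands: what is shown is an unspecified sample whose scheduled version is post-HD, not a proven failure of the rule.

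It is also fair that this is a small, descriptive Phase 1 study and that total Hgb is one of several primary components.

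**Conclusion.** The concern holds. Followed exactly, the plan computes a primary-endpoint change in total Hgb as post-HD minus a value not drawn post-HD at all four on-column timepoints, with no adjustment and no mention of the difference. The bias is towards no fall. On an assumed 5-15% fall in blood volume it is about +0.5 to +1.8 g/dL at 10 g/dL, enough to hide a true loss of 0.5 to 1.5 g/dL. The direction needs only net fluid removal during HD; the size rests on the assumed range. The change tables for free Hgb and haptoglobin are not affected. For the 9 g/dL rules, the finding is that the draw timing is unstated and the scheduled on-column samples are post-HD.

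**What to change.** - **Protocol 15.3:** mark CBC and Hgb at V4, on the post-HD hematology draw already taken there for haptoglobin and free Hgb.
- **SAP 4.7.3:** name the post-HD V4 value as the total-Hgb baseline. The existing rule would select it, but naming it stops a missing V4 from falling back to V1. Keep V1 in the listing only.
- **V23:** state when the Hgb sample is drawn, and compare it only with a value drawn at the same point relative to HD.
- **Protocol 5.2, 17.1.1 and 17.1.2:** state whether the 9 g/dL limits use pre- or post-HD Hgb, and use the same timing throughout.
- **If V4 samples can no longer be added:** do not present change from V1 as the primary Hgb result. Report the post-HD values by combination and label the timing difference on the table.

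The cost is two schedule marks, a small extra blood volume at V4 and a few sentences. One residual remains: V4 is the third session of its study week and the on-column draws fall on the second, so the cancellation is only as good as the similarity of fluid removal between those sessions. Tabulating fluid removed beside the Hgb change would let a reader judge that.
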